| 
Statistical Methodology
 | 
For the primary aim, a linear mixed model analysis of repeated measures will be used to evaluate the repetitive transcranial magnetic stimulation (rTMS) by biomarker status interaction effect on depression severity (CDRS-R score) over 6 weeks of rTMS.
 
For the secondary aim, a within-participant linear mixed model analysis of repeated measures will be used to examine the change in ICF over 6 weeks of rTMS.
 
For the exploratory aims, a within-subjects linear mixed model analysis of repeated measures will be used to examine the change in cortical MRS measures of GABA, glutamate, and glutamine over 6 weeks of rTMS treatment in depressed adolescents. A multiple mediation/moderation path analytic model will be used to estimate the direct effect as well as the total and specific indirect effects of rTMS treatment on depression severity (at the 6-week endpoint) through each potential baseline moderator (anhedonia and adversity).
 |

1 Introduction

This document is a protocol for a human research study. This study will be carried out in accordance with the procedures described in this protocol, applicable United States government regulations and Mayo Clinic policies and procedures.

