- 6 weeks of 10 Hz rTMS will have greater efficacy (assessed by improvement in CDRS-R) than 6 weeks of 1 Hz rTMS in adolescents with low baseline ICF.

Aim 2 examines changes in weekly ICF and CDRS-R across 6 weeks of either 1 Hz or 10 Hz rTMS.

- We anticipate that ICF measures will decrease in depressed adolescents receiving 6 weeks of 1 Hz rTMS.
- We anticipate that ICF measures will increase in depressed adolescents receiving 6 weeks of 10 Hz rTMS.
- Depressive symptom improvement will have a direct relationship with ICF decrease in depressed adolescents receiving 6 weeks of 1 Hz rTMS and an indirect relationship with ICF increase in depressed adolescents receiving 10 Hz rTMS.

Exploratory Aim 3

Aim 3a: To compare 7 T MRS cortical measures of GABAergic tone and glutamatergic neurochemistry in depressed adolescents and healthy control adolescents.

Aim3b: To examine potential changes in cortical GABAergic and glutamatergic neurochemistry after a six week course of either 1 Hz or 10 Hz rTMS in depressed adolescents.

Hypothesis:

1. Depressed adolescents will have decreased cortical levels of GABA as assessed with 7 T MRS compared to healthy control adolescents.
2. Depressed adolescents will have increased cortical levels of Glutamate as assessed with 7 T MRS compared to healthy control adolescents.
3. Bilateral cortical 7 T MRS measures of GABA will increase after 6 weeks of 1 Hz rTMS in depressed adolescents.
4. Bilateral cortical 7 T MRS measures of Gln/Glu will decrease after 6 weeks of 1 Hz rTMS in depressed adolescents.
5. Bilateral cortical 7 T MRS measures of GABA will decrease after 6 weeks of 10 Hz rTMS in depressed adolescents.
6. Bilateral cortical 7 T MRS measures of Gln/Glu will increase after 6 weeks of 10 Hz rTMS in depressed adolescents.

Exploratory Aim 4 examines clinical moderators of treatment (anhedonia and adversity) in this sample of adolescents undergoing treatment with 1 Hz and 10 Hz rTMS.

Hypothesis:

6 weeks of low frequency (1 Hz) rTMS vs. high frequency (10 Hz) rTMS will have greater efficacy (as assessed by CDRS-R) in depressed adolescents with anhedonia and adversity compared to depressed adolescents without anhedonia and adversity

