2.2 Secondary Objective

Aim 2 examines changes in weekly ICF and CDRS-R across 6 weeks of either 1 Hz or 10 Hz rTMS.

- We anticipate that ICF measures will decrease in depressed adolescents receiving 6 weeks of 1 Hz rTMS.
- We anticipate that ICF measures will increase in depressed adolescents receiving 6 weeks of 10 Hz rTMS.

Depressive symptom improvement will have a direct relationship with ICF decrease in depressed adolescents receiving 6 weeks of 1 Hz rTMS and an indirect relationship with ICF increase in depressed adolescents receiving 10 Hz rTMS.

Exploratory Aim 3

Aim 3a: To compare 7 T MRS cortical measures of GABAergic tone and glutamatergic neurochemistry in depressed adolescents and healthy control adolescents.

Aim3b: To examine potential changes in cortical GABAergic and glutamatergic neurochemistry after a six week course of either 1 Hz or 10 Hz rTMS in depressed adolescents.

Hypothesis:

1. Depressed adolescents will have decreased cortical levels of GABA as assessed with 7 T MRS compared to healthy control adolescents.
2. Depressed adolescents will have increased cortical levels of Glutamate as assessed with 7 T MRS compared to healthy control adolescents.
3. Bilateral cortical 7 T MRS measures of GABA will increase after 6 weeks of 1 Hz rTMS in depressed adolescents.
4. Bilateral cortical 7 T MRS measures of Gln/Glu will decrease after 6 weeks of 1 Hz rTMS in depressed adolescents.
5. Bilateral cortical 7 T MRS measures of GABA will decrease after 6 weeks of 10 Hz rTMS in depressed adolescents.

6. Bilateral cortical 7 T MRS measures of Gln/Glu will increase after 6 weeks of 10 Hz rTMS in depressed adolescents.

Exploratory Aim 4 examines clinical moderators of treatment (anhedonia and adversity) in this sample of adolescents undergoing treatment with 1 Hz and 10 Hz rTMS.

Hypothesis:

6 weeks of low frequency (1 Hz) rTMS vs. high frequency (10 Hz) rTMS will have greater efficacy (as assessed by CDRS-R) in depressed adolescents with anhedonia and adversity compared to depressed adolescents without anhedonia and adversity

The proposed project will examine an rTMS dosing, target engagement strategy for adolescent depression and refine understanding of GABAergic and glutamatergic contributions to negative valence. Findings will inform the clinical dissemination of rTMS for adolescent depression and provide insights to further treatment innovation for disorders of the negative valence systems domain early in life.^{9,52}

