3.1 General Design

Phase I will enroll a cohort (N=120) of adolescents (ages 12-18) with clinically significant depression defined as 40 or greater on the Children’s Depression Rating Scale-Revised (CDRS-R). Participants will be stratified according to baseline ICF (high defined as > 1.5 or low defined ≤ 1.5) and then randomized to 6 weeks of either left prefrontal 1 Hz or 10 Hz rTMS. The research team will collect weekly ICF and CDRS-R measures during treatment. We will assess baseline anhedonia with a composite measure from relevant CDRS-R and Beck Depression Inventory-II (BDI-II) items. We will assess lifetime adversity with the Childhood Trauma Questionnaire (CTQ). Participants will have baseline neurocognitive testing. Participants will have a six month follow-up visit with depression severity measures (CDRS-R and BDI-II) and neurocognitive assessments.

Up to 100 Depressed adolescents will be offered the opportunity to undergo magnetic resonance spectroscopy (MRS) measure at baseline (prior to any Phase I TMS treatment) and posttreatment visits (within 2 months after 6 weeks of TMS treatment in Phase I). A comparison group of 30 healthy control adolescents will be offered the opportunity to undergo MRS at one time point. A subset of up to 50 depressed adolescents who do not respond to Phase I TMS treatment will be offered the opportunity to continue in Phase II (within 2 months of completion of Phase I treatment) for two weeks of either iTBS if (ICF ≤ 1.5) or cTBS if (ICF is >1.5).

Magnetic Resonance Imaging: Depressed and control participants will undergo 3 T structural MRI and ultra-high field (7 T) MRS (7-T, 90-cm horizontal bore magnet interfaced with a Siemens console) to examine GABA, glutamate, and glutamine concentrations in the occipital cortex (OCC). [name] is a co-investigator on this grant and will supervise the collection and analyses of all MRI/MRS data at the Center for Magnetic Resonance Research (CMRR) at the University of Minnesota. Please note that travel time from Mayo Clinic Rochester to the CMRR is approximately 1 hour. Participants will be remunerated for travel and all study visits.

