A linear mixed model repeated measures analysis similar to that described above will also be used to examine the relationship between measures of ICF (as the response variable) and depressive symptoms (CDRS-R total as a time-varying covariate) over the 6 weeks of rTMS treatment. We will consider the inclusion of pubertal state and treatment resistance (as defined by ATHF) during the study period as a covariate in the mixed model. The parameter estimates (regression coefficients) will be interpreted from the solution for fixed effects in the mixed model analysis for those who receive 6 weeks of low frequency (1 Hz) rTMS treatment (Hypothesis 2b) and for those who receive 6 weeks of high frequency (10 Hz) rTMS treatment (Hypothesis 2d). A separate linear mixed model analysis similar to that described above will also be implemented over 6 weeks of acute rTMS treatment and throughout the 6-month follow-up period. A nonlinear mixed model will be considered to estimate ICF over the 6 weeks of rTMS treatment from CDRS-R total (if the pattern of ICF and CDRS-R total suggests that a nonlinear model is deemed necessary).

Data Analysis Plan for Exploratory Aim 3 (MRI/MRS)

A within-participants linear mixed model analysis of repeated measures will be used to examine baseline differences between depressed adolescents and healthy control adolescents (Hypotheses 1 and 2); and the change in cortical MRS measures of GABA and Gln/Glu over 6 weeks of rTMS treatment in depressed adolescents. Separate mixed models will be conducted on cortical GABA and Gln/Glu for those who receive 6 weeks of low frequency (1 Hz) rTMS treatment

(Hypotheses 3 and 4) and for those who receive 6 weeks of high frequency (10 Hz) rTMS treatment (Hypotheses 5 and 6). A nonlinear mixed model will be considered (if the pattern of GABA and Gln/Glu values suggests that a nonlinear model is deemed necessary).

Data Analysis Plan for Exploratory Aim4

Moderator Effects of Anhedonia and Adversity on Treatment Outcome of Depression Severity

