The multiple mediation/moderation path analytic model, as described in Preacher and Hayes will be used to estimate the direct effect as well as the total and specific indirect effects of rTMS treatment on depression severity (at the 6-week endpoint) through each of the potential baseline moderators (anhedonia and adversity) operating in parallel and, via a separate model, in serial, while controlling for any potential demographics/patient characteristics (not designated as mediators/moderators), including pubertal state and treatment resistance (as defined by ATHF score). A test of the indirect effects will be conducted by bootstrapping standard errors and confidence intervals (95% bias-corrected) from 5,000 bootstrap samples. The procedures of the PROCESS computational SAS macro developed by Hayes will be used to implement the path analytic-based multiple mediation/moderation model.

Sensitivity Analysis

In this section we present a brief sensitivity analysis plan to address incomplete response patterns according to a missing not at random mechanism. First, we will follow the outcome-based model framework of for longitudinal data with non-random missingness along with a model-based approach proposed for modeling both the treatment response and the missing data process.⁹⁰ That is, if deemed necessary, we will build longitudinal models for the data which includes a model for the dropout (or missing data) process so as to assess the sensitivity of the results about the dependence between dropout (or missingness) and treatment response. Additionally, if deemed necessary, we will consider implementing the semi-parametric shared parameter model approach as described in Tsonaka et al. (2009) to handle nonmonotonic nonignorable missingness for mixed-effects models. A Pattern-Mixture Model will also be considered (if necessary).⁹⁰ The results from such (non-random dropout/missingness) models will then be compared with the results of the proposed standard methods (dropout or missing at random models) so as to assess the sensitivity of the results to the effect of dropouts (or incomplete response patterns according to a missing not at random mechanism).

8 Safety and Adverse Events

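### Exploratory Aim 4 asks a moderation question, but its only stated test is of indirect effects through baseline variables, which randomisation makes zero whatever the moderation

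*Combined protocol and SAP*

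**What the plan says.** The aim is framed as moderation throughout. Section 1.5.1 states that "Exploratory Aim 4 examines clinical moderators of treatment (anhedonia and adversity"). Section 2.2 gives the hypothesis that 1 Hz relative to 10 Hz stimulation "will have greater efficacy (as assessed by CDRS-R) in depressed adolescents with anhedonia and adversity compared to depressed adolescents without anhedonia and adversity". In Section 7.2 the analysis plan carries the heading "Moderator Effects of Anhedonia and Adversity on Treatment Outcome of Depression Severity".

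The analysis described under that heading is a path model. It estimates the direct effect of treatment, the total indirect effect, and the "specific indirect effects of rTMS treatment on depression severity (at the 6-week endpoint) through each of the potential baseline moderators (anhedonia and adversity"), with the two variables arranged in parallel and, in a separate model, in series. The one test stated is this: "A test of the indirect effects will be conducted by bootstrapping standard errors and confidence intervals (95% bias-corrected) from 5,000 bootstrap samples". A SAS macro "will be used to implement the path analytic-based multiple mediation/moderation model". No equation, interaction term or macro model number is given.

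The Statistical Methodology entry of the Study Summary repeats the estimand: "indirect effects of rTMS treatment on depression severity (at the 6-week endpoint) through each potential baseline moderator (anhedonia and adversity"). It has no bootstrap or parallel/serial text.

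For contrast, the Aim 1 plan in Section 7.2 names its treatment-by-ICF-status interaction, lists the fixed effects and describes the simple-effect contrasts.

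**The concern.** A moderator changes the size of the treatment difference. A mediator is changed by treatment and passes part of the effect on. The Aim 4 hypothesis is of the first kind; the stated quantities and test are of the second. The direct effect, also listed, is the treatment coefficient with the other variables held fixed, so it is not a moderation quantity either.

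If the plan is followed as written, a null indirect effect says nothing about whether anhedonia or adversity changes the 1 Hz versus 10 Hz contrast. A significant one would reflect chance baseline imbalance or selective dropout, yet it could be read as evidence about which adolescents benefit from which frequency. Both variables feature strongly in the scientific rationale (Sections 1.1 and 1.5.1), so the result is likely to be used.

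**Working it through.** **Step 1: timing.** Section 3.1 says: "We will assess baseline anhedonia with a composite measure from relevant CDRS-R and Beck Depression Inventory-II (BDI-II) items". Table 2 has the Childhood Trauma Questionnaire collected at baseline. Section 4.3 places randomisation after baseline measurements are complete. Both variables therefore precede treatment assignment.

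**Step 2: the indirect effect.** For treatment T, baseline variable M and outcome Y, the indirect effect is a × b, where a = E[M | T = 1] − E[M | T = 0] and b is the M-to-Y coefficient. Randomisation after M is measured gives a = 0, so a × b = 0 for any b. In the serial model the effect is a × (M1-to-M2 path) × b, again zero. The treatment-by-moderator coefficient k enters neither expression, so the result holds at every k.

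**Step 3: size.** The documents give no effect size or power for Aim 4, so there is no stated figure to reproduce and every input below other than sample size is an assumption. There were 2,000 simulated trials per scenario and 1,000 bootstrap resamples each (the plan has 5,000), with bias-corrected 95% intervals.

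- Outcome: Y = m(M1 + M2) + 0.3 B0 + k(T − 0.5)M1 + 1.22(T − 0.5)(ICF − 0.5) + N(0,1). M1 is anhedonia, M2 adversity and B0 baseline CDRS-R, all standard normal. Correlations: M1 with M2 0.3, M1 with B0 0.5, M2 with B0 0.15.
- 1.22 = 2 × 0.61 sets the Section 7.1 effect of 0.61 in opposite directions in the two ICF strata.
- Planned tests adjust for pubertal state and ATHF. The comparator is the test of T × M1 in the model proposed under the fix.
- k is in residual SDs per SD of anhedonia. m = 0 means no direct moderator effect, although anhedonia still relates to Y through B0.

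Rejection rates (%) at two-sided 0.05:

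| Scenario and test | k = 0 | 0.3 | 0.6 | 0.9 |
|---|---|---|---|---|
| **N = 100, m = 0** | | | | |
| Interaction | 4.8 | 28.8 | 76.7 | 97.7 |
| Interaction, FDR over two | 2.6 | 19.1 | 67.9 | 96.1 |
| Indirect, anhedonia | 2.5 | 2.8 | 2.3 | 1.9 |
| Indirect, adversity | 0.4 | 0.5 | 0.9 | 0.6 |
| Indirect, serial | 0.5 | 1.0 | 1.2 | 0.9 |
| **N = 100, m = 0.3** | | | | |
| Interaction | 4.8 | 26.3 | 75.1 | 97.3 |
| Interaction, FDR over two | 2.9 | 17.8 | 66.4 | 95.4 |
| Indirect, anhedonia | 8.5 | 6.8 | 7.5 | 7.1 |
| Indirect, adversity | 5.6 | 7.4 | 6.1 | 5.8 |
| Indirect, serial | 8.0 | 7.2 | 7.7 | 7.0 |
| **120 randomised, dropout, m = 0.3** | | | | |
| Interaction | 4.2 | 22.2 | 69.6 | 95.4 |
| Indirect, anhedonia | 7.6 | 7.6 | 10.0 | 11.3 |
| Mean anhedonia indirect effect (not a rate) | 0.001 | −0.016 | −0.035 | −0.049 |

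Without dropout, mean indirect effects lie within 0.004 of zero at every k. The dropout case has log-odds of −1.60 + 1.0 per SD of worse outcome, which loses 20.7%: 120 × (1 − 0.207) ≈ 95 with a Week 6 value, in line with the roughly 20% dropout in Section 7.1. The small drift there is selection. Section 4.4.1 asks early discontinuers to complete Week 6 procedures, so real missingness may be lower.

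**Step 4: a second simulation.** N = 100, both moderators interacting with treatment, the total indirect effect tested by bootstrap against a joint 2-df F-test of the two interactions (1,000 trials), and no other covariates in either analysis. At slopes of 0, 0.3, 0.5 and 0.8 the indirect test rejected in 5.5%, 5.9%, 7.0% and 6.3% of trials, and the interaction test in 5.6%, 56%, 93% and over 99%. Mean indirect effects ran from −0.003 to 0.004.

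**The case against.** The best defence is that the plan names a combined mediation/moderation model from a cited methods source, runs it with a macro that may accommodate interactions, and heads the section as moderator effects; an intended interaction term cannot be excluded. That stands as a remark on intent. It supplies no specification: every listed quantity is a direct or indirect effect, parallel and serial are mediator layouts, and the only test is of indirect effects.

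The aim is also exploratory and has no sample-size basis. That limits the consequence and is why the primary and secondary conclusions are untouched, but an exploratory analysis still has to address its own hypothesis.

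The simulated power depends on chosen inputs. At a slope of 0.3 it is 26-29% in one set-up and 56% in the other, because the second gives both moderators an interaction and tests them jointly. In the first set-up the two analyses also carry different covariates; in the second they do not, and the pattern is the same. The conclusion rests on Steps 1 and 2, and the figures only illustrate it.

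Finally, the corrected test is weak for modest interactions. That is true, and is a reason to report intervals.

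**Conclusion.** The concern holds. For Exploratory Aim 4 the plan is wrong as written: the stated test targets a quantity that is zero among all randomised participants whatever the moderation, and no moderation test is specified. This follows from the timing of measurement and randomisation and needs no numerical assumption.

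Under the assumptions above, an anhedonia interaction of 0.6 SD per SD would be found in 75-77% of trials by the interaction test (66-68% after FDR). The indirect-effect tests reject in 0.9% to 7.7% of those trials, and not because of the moderation. Outcome-dependent dropout raises the anhedonia indirect test to at most 11.3%. The 95% interval for the interaction has a mean half-width of about 0.44 SD per SD, so an interaction of 0.3 would often not be distinguishable from zero. This should be fixed before analysis.

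**What to change.** In the Aim 4 plan in Section 7.2, replace the indirect-effect, parallel/serial and bootstrap text, and change the matching sentence in the Study Summary. The essential content is both treatment-by-moderator terms, a test and 95% confidence interval for each, and no indirect-effect language for baseline variables. For example:

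*Week 6 CDRS-R will be modelled on treatment, baseline anhedonia composite, CTQ adversity, treatment × anhedonia, treatment × adversity, ICF stratum, treatment × ICF stratum, baseline CDRS-R, pubertal state and ATHF score. The two interaction p-values will be adjusted by the False Discovery Rate. The 1 Hz versus 10 Hz difference will be reported with 95% confidence intervals across the range of each moderator.*

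A repeated-measures model with treatment × moderator × time, all lower-order terms and a Week 6 contrast is a good alternative: it keeps participants with a missing Week 6 value, as the Aim 1 analysis does. Including treatment × ICF is a choice, not a requirement; omitting it lowers power at 0.6 from 75-77% to 71-74%.

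Three points need settling alongside:

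- Whether the hypothesis concerns each moderator separately or both jointly. A joint reading needs anhedonia × adversity and treatment × anhedonia × adversity, and the hypothesis in Sections 1.5.1 and 2.2 should say which is meant.
- Which items form the anhedonia composite, and how the CTQ is scored (total, subscale or cut-off).
- That the composite shares items with baseline CDRS-R, which should be acknowledged when both are in the model.

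The cost is a wording change and these definitions. No new data are needed.

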8.1 Definitions

Unanticipated Adverse Device Effect (UADE)

A UADE is any serious adverse effect on health or safety or any life-threatening problem or death caused by, or associated with, a device if that effect, problem or death was not previously identified in nature, severity, or degree of incidence in the investigational plan or IDE application (including a supplementary plan or application), or any other unanticipated serious problem associated with a device that relates to the rights, safety, or welfare of participants.

Adverse Effect (Event)

Any untoward medical occurrence in a participant involved in clinical study of an investigational device; regardless of the causal relationship of the problem with the device or, if applicable, other study related treatment(s).

Associated with the investigational device: there is a reasonable possibility that the adverse effect may have been caused by the investigational device.

Life-threatening adverse effect: Any adverse effect that places the participant, in the view of either the investigator or the sponsor, at immediate risk of death from the effect **as it occurred**. It does not include a reaction that, had it occurred in a more severe form, might have caused death.

Serious adverse effect: An adverse effect is considered “serious” if, in the view of either the investigator or the sponsor, it results in any of the following outcomes:

- death
- a life-threatening AE
- inpatient hospitalization or prolongation of existing hospitalization
- a persistent or significant disability/incapacity
- a congenital anomaly/birth defect.

Unanticipated adverse effect: Any adverse effect, the nature, specificity, severity, or frequency of which is not consistent with the risk information in the clinical study protocol or elsewhere in the current IDE application.

General Physical Examination Findings

At screening, any clinically significant abnormality should be recorded as a preexisting condition. At the end of the study, any new clinically significant findings/abnormalities that meet the definition of an adverse event must also be recorded and documented as an adverse event.

Hospitalization, Prolonged Hospitalization or Surgery

Any adverse event that results in hospitalization or prolonged hospitalization should be documented and reported as an unanticipated adverse device effect unless specifically instructed otherwise in this protocol. Any condition responsible for surgery should be documented as an adverse event if the condition meets the criteria for an adverse event.

Neither the condition, hospitalization, prolonged hospitalization, nor surgery are reported as an adverse event in the following circumstances

- Hospitalization or prolonged hospitalization for diagnostic or elective surgical procedures for a preexisting condition. Surgery will **not** be reported as an outcome of an adverse event if the purpose of the surgery was elective or diagnostic and the outcome was uneventful
- Hospitalization or prolonged hospitalization for therapy of the target disease of the study, unless it is a worsening or increase in frequency of hospital admissions as judged by the clinical investigator.

Post-study Adverse Event

All unresolved adverse events should be followed by the investigator until the events are resolved, the Participant is lost to follow-up, or the adverse event is otherwise explained. At the last scheduled visit, the research team will instruct each participant to report any subsequent event(s) that the participant, or the participant's personal physician, believes might reasonably be related to participation in this study.

Preexisting Condition

A preexisting condition is one that is present at the start of the study. A preexisting condition should be recorded as an adverse event if the frequency, intensity, or the character of the condition worsens during the study period.

Unanticipated Problems Involving Risk to Participants or Others (UPIRTSO)

Any unanticipated problem or adverse event that meets all of the following three criteria:

- **Serious:** Serious problems or events that results in significant harm, (which may be physical, psychological, financial, social, economic, or legal) or increased risk for the Participant or others (including individuals who are not research Participants). These include: (1) death; (2) life threatening adverse experience; (3) hospitalization - inpatient, new, or prolonged; (4) disability/incapacity - persistent or significant; (5) birth defect/anomaly; (6) breach of confidentiality and (7) other problems, events, or new information (i.e. publications, DSMB reports, interim findings, product labeling change) that in the opinion of the local investigator may adversely affect the rights, safety, or welfare of the Participants or others, or substantially compromise the research data, **AND**
- **Unanticipated:** (i.e. unexpected) problems or events are those that are not already described as potential risks in the protocol, consent document, not listed in the Investigator's Brochure, or not part of an underlying disease. A problem or event is "unanticipated" when it was unforeseeable at the time of its occurrence. A problem or event is "unanticipated" when it occurs at an increased frequency or at an increased severity than expected, **AND**
- **Related:** A problem or event is "related" if it is possibly related to the research procedures.

An *adverse event* is any untoward, undesired, or unplanned event in the form of signs, symptoms, disease, or laboratory or physiological observations occurring in a person who has received NeuroStar TMS therapy (1 Hz, 10 Hz, cTBS, or iTBS). The event need not be causally related to the NeuroStar device or the present clinical trial. An AE includes, but is not limited to:

- Any clinically significant worsening of a pre-existing condition;
- An AE occurring from overdose (i.e., a dose higher than that described in the protocol) of a NeuroStar TMS device, whether accidental or intentional;
- An AE occurring from abuse (e.g., use for non-clinical reasons) of a NeuroStar TMS device;
- An AE that has been associated with the discontinuation of the use of a NeuroStar TMS device; a *preexisting condition* is a clinical condition (including a condition being treated)

that is diagnosed before an informed consent form is signed and is documented as part of the Participant's medical history.

The questions concerning whether the condition existed before the start of the active phase of the study and whether it has increased in severity and/or frequency will be used to determine whether an event is a treatment-emergent AE (TEAE). An AE is considered to be a TEAE if (1) it was not present when the active phase of the study began and is not a chronic condition that is part of the Participant's medical history, or (2) it was present at the start of the active phase of the study or as part of the Participant's medical history, but the severity or frequency increased during the active phase.

Additionally, *important medical events* that may not result in death, be life-threatening, or require hospitalization, may be considered SAEs, based upon appropriate medical judgment.

Life threatening refers to immediate risk of death as the event occurred or use or continued use of the device or other medical product might have resulted in the death per the reporter. A life-threatening event does not include an event that, had it occurred in a more severe form, might have caused death, but as it actually occurred, did not create an immediate risk of death.

Hospitalization is to be considered only as an admission. Hospitalization or prolongation of a hospitalization constitutes an AE to be classified as serious.

Note that hospitalizations planned before the start of the study, for a preexisting condition that has not worsened, do not constitute an SAE (e.g., elective hospitalization for surgery due to a preexisting condition that has not worsened during the study).

If there is any doubt whether the information constitutes an SAE, the information should be treated as an SAE for the purpose of this study.

